### 5.6.2.1 Overall Safety Summary

An overall summary of AEs will be presented using the Extended Set to catch AEs of subjects who did not receive at least one injection of contrast agent. The table will be presented with the overall “Total” column only with the following variables:

- Total number of AEs.
- Total number of subjects with at least one AE.
- Distribution of the number of AEs reported by subject (0, 1, 2 or 3 or more AEs).
- Total number of Serious AEs (SAEs) (variable “serious” classified as yes or missing).
- Total number of subjects with at least one SAE.
- Total number of AEs according to intensity.
- Total number of subjects with at least one AE according to intensity (subjects with AEs having different intensities will be counted in each category of intensity).
- Total number of AEs according to the outcome.
- Total number of subjects with at least one AE according to the outcome (subjects with AEs having different outcomes will be counted in each category of outcome).
- Total number of AEs requiring a concomitant drug (other action taken).
- Total number of subjects with at least one AE requiring a concomitant drug (other action taken).

The same table will be displayed by dose of P03277 and period for Treatment Emergent AEs (TEAEs) using the Safety Set. The terms "AE" will be replaced by "TEAE". The following variables will be also presented:

- Total number of TEAEs with causal relationship to the IMP.
- Total number of subjects with at least one TEAE with causal relationship to the IMP.
- Total number of TEAEs requiring withdrawal of study contrast agent (action taken).
- Total number of subjects with at least one TEAE requiring withdrawal of study contrast agent (action taken).

The tables that will be displayed are detailed in Section 6.1.3.2.1.

### 5.6.2.2 TEAES

The number and percentage of subjects with at least one TEAE will be presented using the Safety Set by dose of P03277 and period according to Primary SOC and PT.

The table will be sorted by descending frequency of SOC and, within each SOC by descending frequency of PT.

The table that will be displayed is detailed in Section 6.1.3.2.2.

### 5.6.2.3 TEAEs with Causal Relationship to the IMP

The number and percentage of subjects with at least one TEAE with causal relationship to the IMP will be presented by dose of P03277 and period according to Primary SOC and PT. AEs with causal relationship to the IMP are those described by the investigator with causal relationship to the IMP “related” or as AEs with unassessable relationship.

CONFIDENTIAL	FORM  STATISTICAL ANALYSIS PLAN N° GDX-44-004  VERSION 1.0      DATED: 09JAN2018	[REDACTED]
		[REDACTED]

The table that will be displayed is detailed in Section 6.1.3.2.3.

#### 5.6.2.4 TEAEs with Causal Relationship to a Study Procedure

The number and percentage of subjects with at least one TEAE with causal relationship to a study procedure will be presented by dose of P03277 and period according to Primary SOC and PT. AEs with causal relationship to a study procedure are those described by the investigator with causal relationship to a study procedure “related” or as AEs with unassessable relationship.

The table that will be displayed is detailed in Section 6.1.3.2.4.

The listings that will be displayed on AEs and TEAEs are detailed in Section 6.2.7. They will present a complete description of the AE by Primary SOC, Lowest Level Term (LLT), PT and description, including date/time of onset, end date, duration, intensity, seriousness, causal relationship to the IMP, causal relationship to a study procedure, withdrawal of study contrast agent (action taken), concomitant drug (other action taken) and the outcome. The displayed duration of an AE will be computed in days using the following formula: event end date - date/time of onset + 1. In case one of the dates is missing or incomplete then the duration will be missing. The listings will be sorted by contrast agent group, subject number, date/time of onset, end date, Primary SOC, PT and description.

#### 5.6.3. Deaths, serious adverse events and other significant adverse events

Deaths, if any, will be listed in Table 14.3.2.6. SAEs will be listed in Table 14.3.2.7. These listings will be sorted by contrast agent group, subject number, date/time of onset, end date, Primary SOC, LLT, PT and description.

#### 5.6.4. Clinical laboratory evaluation

*Hematology data* from central laboratory include the following parameters (in SI and conventional units):

	SI units	Conventional units
Red Blood Cells (RBC) = Erythrocytes	$10^{12}/L$	$10^6/\mu L$
White Blood Cells (WBC) = Leukocytes	$10^9/L$	$10^3/\mu L$
Neutrophils	$10^9/L$	$10^3/\mu L$
Neutrophils/Total Cells	%	%
Eosinophils	$10^9/L$	$10^3/\mu L$
Eosinophils/Total Cells	%	%
Basophils	$10^9/L$	$10^3/\mu L$
Basophils/Total Cells	%	%
Lymphocytes	$10^9/L$	$10^3/\mu L$
Lymphocytes/Total Cells	%	%
Monocytes	$10^9/L$	$10^3/\mu L$

CONFIDENTIAL

FORM

[REDACTED]

## STATISTICAL ANALYSIS PLAN N° GDX-44-004

Page 42 / 60

VERSION 1.0

DATED: 09JAN2018

[REDACTED]

	SI units	Conventional units
Monocytes/Total Cells	%	%
Platelet count	10  /L	10  /µL
Hemoglobin	g/L	g/dL
Hematocrit	v/v	%
Mean Corpuscular Volume (MCV)	fL	fL

*Biochemistry data* from central laboratory include the following parameters:

	SI units	Conventional units
Sodium	mmol/L	mEq/L
Potassium	mmol/L	mEq/L
Chloride	mmol/L	mEq/L
Glucose	mmol/L	mg/dL
Blood Urea Nitrogen (BUN)	mmol/L	mg/dL
Urea	mmol/L	mg/dL
Serum creatinine	umol/L	mg/dL
eGFR	mL/min/1.73m 	mL/min/1.73m 
Total protein	g/L	g/dL
Calcium	mmol/L	mg/dL
Phosphorus	mmol/L	mg/dL
Total bilirubin	umol/L	mg/dL
Indirect bilirubin	umol/L	mg/dL
Conjugated bilirubin	umol/L	mg/dL
Aspartate Amino Transferase (AST)	U/L	U/L
Alanine Amino Transferase (ALT)	U/L	U/L
Alkaline Phosphatase	U/L	U/L
Lactate DeHydrogenase (LDH)	U/L	U/L
Triglycerides	U/L	U/L
Cystatin C	U/L	U/L

Hematology and biochemistry parameters at visits 2, 3, 4 and 5 will be described as quantitative variables in both SI and conventional units. Numbers and percentages of subjects with values out of range (lower than the lower limit or higher than the upper limit of quantification) will also be presented, except if values for normal ranges are unknown for a parameter.

Erythrocytes, neutrophils, eosinophils, basophils, lymphocytes, monocytes, hemoglobin and hematocrit (hematology) and potassium, chloride, BUN, urea, total protein, phosphorus, total bilirubin, AST, ALT, alkaline phosphatase, triglycerides and cystatin C (biochemistry) will be separately described by gender.

## STATISTICAL ANALYSIS PLAN N° GDX-44-004

Page 43 / 60

VERSION 1.0

DATED: 09JAN2018

[REDACTED]

Change from baseline in *serum creatinine, eGFR, BUN and cystatin C* will be computed and described at visits 3, 4 and 5 in both SI and conventional units. The baseline value for each laboratory parameter will be the last value measured before the contrast agent administration (i.e. the assessment prior to 1st MRI).

Shift tables presenting relative change from baseline in classes *versus* baseline in classes will be displayed for *serum creatinine, eGFR, BUN and cystatin C*.

Baseline data will be classified as follows (no baseline categories will be used for cystatin C):

SI units	Conventional units

• Serum creatinine (umol/L):

○ < 20

○ <math>\geq 20</math> and < 40

○ <math>\geq 40</math> and < 60

○ <math>\geq 60</math>

• eGFR (mL/min/1.73m^2):

○ < 100

○ <math>\geq 100</math> and < 150

○ <math>\geq 150</math> and < 200

○ <math>\geq 200</math>

• BUN (mmol/L):

○ < 2

○ <math>\geq 2</math> and < 4

○ <math>\geq 4</math> and < 6

○ <math>\geq 6</math>

	

• Serum creatinine (mg/dL):

○ < 0.22

○ <math>\geq 0.22</math> and < 0.44

○ <math>\geq 0.44</math> and < 0.66

○ <math>\geq 0.66</math>

• eGFR (mL/min/1.73m^2):

○ < 100

○ <math>\geq 100</math> and < 150

○ <math>\geq 150</math> and < 200

○ <math>\geq 200</math>

• BUN (mg/dL):

○ < 12

○ <math>\geq 12</math> and < 24

○ <math>\geq 24</math> and < 36

○ <math>\geq 36</math>

Relative change from baseline will be calculated as follows:  $100^* \text{ (post injection measurement - baseline measurement) / baseline measurement}$ . Relative change from baseline will be classified as follows:

- $\leq -50\%$ .
- $> -50\%$  and  $\leq -25\%$ .
- $> -25\%$  and  $\leq -15\%$ .
- $> -15\%$  and  $< 0\%$ .
- $\geq 0\%$  and  $< 15\%$ .
- $\geq 15\%$  and  $< 25\%$ .
- $\geq 25\%$  and  $< 50\%$ .
- $\geq 50\%$ .

Numbers and percentages of subjects in each class will be presented in both SI and conventional units for centrally analyzed data only.

Urinalysis data will be only listed.

CONFIDENTIAL	FORM	
STATISTICAL ANALYSIS PLAN N° GDX-44-004		Page 44 / 60
VERSION 1.0      DATED: 09JAN2018		

The tables and listings that will be displayed are detailed in Sections 6.1.3.3 and 6.2.8 respectively.

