### **Laboratory data**

The statistical analysis will present results in standard international units and United States units. Original units will be only listed. Laboratory data will be analyzed quantitatively and qualitatively. Qualitative analyses will be done via comparison of laboratory data to their reference ranges and according to their clinical significance. Quantitative analyses will be done by tabulating raw data and change from baseline. They will be displayed qualitatively as well by means of shift tables.

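### SAP 5.6.4 converts the BUN baseline classes to mg/dL with the urea factor, so the SI and conventional shift tables place most of the BUN range in different rows

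*SAP*

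**What the plan says.** SAP 5.6.4 calls for "Shift tables presenting relative change from baseline in classes", crossed with baseline class, for serum creatinine, eGFR, BUN and cystatin C. The limits follow the words "Baseline data will be classified as follows (no baseline categories will be used for cystatin C". They are:

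- BUN: 2, 4 and 6 mmol/L; 12, 24 and 36 mg/dL.
- Serum creatinine: 20, 40 and 60 µmol/L; 0.22, 0.44 and 0.66 mg/dL.
- eGFR: 100, 150 and 200 mL/min/1.73 m² in both columns.

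Both unit systems are to be reported: "Numbers and percentages of subjects in each class will be presented in both SI and conventional units for centrally analyzed data only". BUN and urea have separate rows in the biochemistry list of the same section, each in mmol/L and mg/dL, and both appear again among the parameters to be described by gender: "potassium, chloride, BUN, urea, total protein, phosphorus, total bilirubin".

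For all haematology and biochemistry parameters, SAP 5.6.4 also counts subjects with out-of-range values, which it defines as "lower than the lower limit or higher than the upper limit of quantification". The sentence then makes an exception for parameters whose normal ranges are not known. Protocol section 12.4 (Laboratory data) says: "Qualitative analyses will be done via comparison of laboratory data to their reference ranges".

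**The concern.** Two tables of the same subjects, differing only in units, should have the same row totals. If the limits in one column are not the converted limits of the other, the study report will show two different baseline distributions of BUN, and each shift will be set against a different baseline level depending on the table read. The BUN limits look like a conversion of urea rather than of urea nitrogen, which would put the conventional limits at about twice the intended level.

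The out-of-range definition raises a separate question. A limit of quantification is a property of the assay. Taken literally, counting values beyond it would leave out results that are abnormal but measurable, across every haematology and biochemistry parameter.

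**Working it through.** **Inputs.** The class limits are from SAP 5.6.4. The creatinine unit pair, 0.5 mg/dL = 44 µmol/L, is from the stopping rule in protocol section 11.2. The documents give no molar masses. I assume the values that follow from atomic weights: urea 60.06 g/mol, and the two nitrogen atoms in urea 28.01 g/mol.

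**Formula.** mg/dL = mmol/L × molar mass / 10.

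**Reproducing the SAP's BUN limits from 2, 4 and 6 mmol/L.**

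| Basis | Factor | Result, mg/dL | Against 12, 24, 36 |
|---|---|---|---|
| Urea | 6.006 | 12.01, 24.02, 36.03 | within 0.1% |
| Urea nitrogen (two N) | 2.801 | 5.60, 11.21, 16.81 | 53% lower |
| Single nitrogen atoms | 1.401 | 2.80, 5.60, 8.40 | 77% lower |

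Only the urea factor gives the printed limits. For a row labelled BUN they are 6.006 / 2.801 = 2.14 times too high.

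**Converting back.** As urea nitrogen, 12, 24 and 36 mg/dL are 12 / 2.801 = 4.28, 24 / 2.801 = 8.57 and 36 / 2.801 = 12.85 mmol/L. Setting these beside the SI limits gives the baseline class in each table:

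| Baseline BUN, mmol/L | SI class | Conventional class |
|---|---|---|
| below 2 | 1 | 1 |
| 2 to <4 | 2 | 1 |
| 4 to <4.28 | 3 | 1 |
| 4.28 to <6 | 3 | 2 |
| 6 to <8.57 | 4 | 2 |
| 8.57 to <12.85 | 4 | 3 |
| 12.85 and above | 4 | 4 |

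The tables agree only below 2 and from 12.85 mmol/L upward. A subject at 5 mmol/L (5 × 2.801 = 14.0 mg/dL) is in class 3 in one table and class 2 in the other. A subject at 7 mmol/L (19.6 mg/dL) is in classes 4 and 2.

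**Creatinine.** The protocol's pair gives 44 / 0.5 = 88 µmol/L per mg/dL. Then 20 / 88 = 0.227, 40 / 88 = 0.455 and 60 / 88 = 0.682 mg/dL, against 0.22, 0.44 and 0.66 in the SAP. Converting the SAP's figures back gives 0.22 × 88 = 19.4, 0.44 × 88 = 38.7 and 0.66 × 88 = 58.1 µmol/L. Subjects at 19.4 to <20, 38.7 to <40 and 58.1 to <60 µmol/L therefore sit one class higher in the conventional table. This is the same kind of fault on a much smaller scale.

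**Out-of-range values.** No arithmetic applies. The protocol names reference ranges. The SAP sentence names limits of quantification but ends with an exception that makes sense only if the comparison is with normal ranges. Protocol section 7.2.8 also has the central laboratory flag values outside normal ranges. The texts fit together once the word quantification is replaced.

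**The case against.** The best defence on BUN is that the label is wrong and the limits are right. Protocol 7.2.8 lists BUN and urea as a single item, and the SAP's two sets of limits match exactly if the row is urea. Whether any subject changes row then depends on which mg/dL result is tabulated. This stands as far as it goes: the documents do not show which was meant. It does not remove the fault, because the SAP separates the two analytes and prints urea limits under the BUN label. Either the label or the limits must change.

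It is also fair to say that the effect is narrow. Relative change does not depend on units, so the totals in each percent-change class are the same in both tables. Continuous summaries and change from baseline are untouched. The stopping rule in protocol 11.2 uses creatinine and cystatin C, not BUN, and breaches are recorded as deviations under SAP 5.2.2 whatever the baseline class. All of this stands.

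A reader might go further and infer that the eGFR and creatinine classes fail to separate the eligible adults. The documents do not support that. Eligibility requires an eGFR of at least 60, and the cut at 100 lies inside the eligible range and divides it. Local eGFR below 60 is counted at Visits 2 and 4 under SAP 5.4.5, and local or central values below 60 with contrast given are listed deviations in SAP 5.2.2. It is true that no creatinine cut lies above 60 µmol/L, but neither document gives a distribution of creatinine, so how many subjects would share the top class cannot be stated. Finer classes are a choice of presentation.

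A reader might also conclude that abnormal laboratory values will be missed. That follows only from a literal reading, which the rest of the SAP's own sentence contradicts. It is better described as a wording error to correct.

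**Conclusion.** The point holds for the BUN row. The conventional limits are the SI limits multiplied by the urea factor, and for urea nitrogen they are 2.14 times too high. Every baseline BUN from 2.0 to below 12.85 mmol/L falls in a different baseline row in the two tables: two rows apart for 4.0 to <4.28 and 6.0 to <8.57 mmol/L, and one row apart elsewhere in that range. This rests on two assumptions: that BUN in mg/dL means urea nitrogen, as the name and the separate urea row imply, and that the molar masses above apply. The number of subjects affected cannot be given, because the documents contain no expected BUN distribution.

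The creatinine mismatch is real but confined to narrow bands just below each limit. The out-of-range definition conflicts with the protocol and with its own sentence, and should be reworded.

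The importance is low. These are descriptive safety tables, only the allocation to baseline rows is wrong, and no efficacy result or stopping decision depends on it. It is still worth correcting, since the report would otherwise contain two renal tables that disagree about the same subjects.

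**What to change.** In SAP 5.6.4:

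1. Set the conventional BUN limits to 5.6, 11.2 and 16.8 mg/dL. Alternatively, keep 12, 24 and 36 mg/dL, relabel the row as urea in both columns, and tabulate the urea result.
2. State that each subject's baseline class is derived once, from one unit system, and carried into both tables. This also removes disagreements caused by rounded limits.
3. Align the creatinine mg/dL limits with 20, 40 and 60 µmol/L: about 0.23, 0.45 and 0.68.
4. Define out-of-range values by the laboratory's normal (reference) range in place of the limit of quantification, as in protocol 12.4.

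An eGFR cut at the trial's own limit of 60 could be added but is optional. The cost is a few edits to SAP text and table programs. No new data are needed, and no other analysis changes.

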### 5.6.5. Vital signs, physical findings and other observations related to safety

### 5.6.5.1 ECG

Three values are expected at each time point (triplicate ECG): before injection, 45 ( $\pm 15$  minutes) after injection, between 2 and 4 hours after injection and 1 day after injection (for both injections). The value analyzed will be the mean of the non-missing values obtained from this triplicate ECG.

The QT corrected (QTc) interval will be described, separating QTc Fridericia's and QTc Bazett's. These parameters at each time point will be described as quantitative variables.

Change from baseline in ECG parameters will be computed and described at each post-baseline measurement. The baseline value will be the triplicate ECG measured prior to the injection of the 1st contrast agent.

Numbers and percentages of subjects with values out of range will also be presented, based on a notable QTc > 450 ms, a notable QTc > 500 ms and a notable QTc change from baseline > 60 ms.

Other ECG parameters than QTc will be listed only.

The tables and the listing that will be displayed are detailed in Sections 6.1.3.4.1 and 6.2.9 respectively.

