For all other laboratory assessments, the central laboratory will flag laboratory values falling outside of the normal ranges on the central laboratory report (which the investigator should review and sign off) and the investigator will report any values considered clinically significant as an AE.

- **Vital signs**

Vital signs (supine systolic and diastolic blood pressures, pulse rate) will be measured and recorded according to the following schedules:

- Immediately prior to each contrast agent injection (baseline value)
- At  $45 \pm 15$  minutes and 2-4 hours following each contrast agent injection
- One day after each contrast injection

If significant changes in vital signs occur, vital signs should be recorded more frequently, and for as long as necessary, to ensure that the changes have been resolved and/or that the subject is stable. All clinically significant abnormal value or change value will be recorded as AEs.

A significant clinically change is defined as follows: Pulse Rate  $< 40$  or  $> 100$  bpm; systolic Blood Pressure  $< 90$  or  $> 160$  mmHg; diastolic Blood Pressure  $> 100$  mmHg.

Blood pressure and pulse rate will be measured after a rest of 10 minutes in supine position. Blood pressure will not be measured on the arm used for the injection.

 CONFIDENTIAL	Protocol No. GDX-44-004 Version No. 2.0 (Protocol including amendment n°1) Date: 11 July , 2016	 Page 40 / 84
----------------------------------------------------------------------------------------------------------	----------------------------------------------------------------------------------------------------------	-----------------------------------------------------------------------------------------------------

- **ECG monitoring**

The following parameters will be collected via an ECG device supplied by the ECG core laboratory: heart rate (RR interval), PR interval, QRS duration, QT, QTc Bazett, QTc Fridericia. The 12-lead ECGs will be measured prior to each contrast injection, and at 45 minutes  $\pm$  15 minutes, at 2-4 hour, and 1 day after each contrast injection.

The ECG measured prior to the 1st contrast injection (at visit 2) will be considered as the baseline evaluation.

[figure not shown]
TriPLICATE ECGs (3 measurements taken at approximately 1 min intervals) will be recorded prior to each MRI and at each post-injection time point.

The subject is to be at rest for at least 5 minutes prior to any ECG recording.

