### **ECG**

ECG data will be analyzed quantitatively and qualitatively. Qualitative analyses will be done via comparison of ECG data to their normal ranges and according to their clinical significant changes. Notable QTc value will be presented for raw data and changes (see [section 7.2.8](#)). Quantitative analyses will be done by tabulating raw data and change from baseline.

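### The SAP summarises only QTc and leaves PR, QRS, uncorrected QT and ECG heart rate to listings, although the protocol promises tables of ECG data; the reduction is not declared

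*SAP*

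**What the plan says.** Protocol 7.2.8 names the measures to be collected: "heart rate (RR interval), PR interval, QRS duration, QT, QTc Bazett, QTc Fridericia". They are recorded in triplicate before each injection and at three times after it.

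Protocol 12.4, under ECG, sets out the analysis in four sentences. The first is general: "ECG data will be analyzed quantitatively and qualitatively". The second covers the qualitative side: "Qualitative analyses will be done via comparison of ECG data to their normal ranges and according to their clinical significant changes". The third adds a specific QTc display: "Notable QTc value will be presented for raw data and changes". The fourth covers the quantitative side: "Quantitative analyses will be done by tabulating raw data and change from baseline".

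SAP 5.6.5.1 is narrower. It opens with "The QT corrected (QTc) interval will be described", separates Fridericia from Bazett, and bases the out-of-range counts on three QTc criteria (above 450 ms, above 500 ms, and a rise of more than 60 ms). It also says "Change from baseline in ECG parameters will be computed and described at each post-baseline measurement". It closes with "Other ECG parameters than QTc will be listed only".

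SAP Section 4, which records departures from the planned analysis, declares two: a restricted repeat of the secondary criteria on the per-protocol set, and three added efficacy criteria. It says nothing about ECG.

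**The concern.** The protocol and the SAP differ on which ECG measures get a summary, and the SAP makes the reduction without saying so. The SAP states that it is based on protocol version 2.0, which is the version containing the ECG commitment, so the amendment does not explain the difference.

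The primary objective is to find a safe as well as an effective dose. SAP 5.5.1.5 bases dose selection on benefit and risk across four doses. A modest dose-related lengthening of PR or QRS shows up in group means and changes by dose, and is easily missed in a subject-level listing. If the SAP is followed as written, nobody choosing the dose will be shown those means.

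**Working it through.** No figure in the plan needs reproducing. The check is a comparison of texts, plus a count of what would sit in listings.

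**Step 1: does the protocol commitment reach beyond QTc?** Yes. Its general sentences refer to ECG data. Notable QTc has its own sentence, which would be redundant if the others already meant QTc alone.

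**Step 2: measure by measure.**

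| Measure (Protocol 7.2.8) | Protocol 12.4 | SAP 5.6.5.1 | Other summary in the SAP text |
|---|---|---|---|
| QTc Fridericia | table | table, change, counts | – |
| QTc Bazett | table | table, change, counts | – |
| Heart rate/RR | table | listing | pulse rate, SAP 5.6.5.2 |
| PR | table | listing | none |
| QRS | table | listing | none |
| QT, uncorrected | table | listing | none |

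So 6 − 2 = 4 of the 6 measures move from table to listing, and 3 of those 4 have no substitute table.

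**Step 3: summary by clinical significance.** The protocol asks for one. SAP 5.6.5.1 describes none; its only categorical output is the QTc counts.

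**Step 4: internal consistency of the SAP.** The change-from-baseline sentence speaks of ECG parameters generally, while the closing sentence limits all but QTc to listings. Both can be true only if the former means QTc. The closing sentence is the more specific and most naturally governs, but the wording needs an edit on either reading.

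**Step 5: can a listing serve instead?** Four time points × 2 injections = 8 per subject, and 8 × 3 tracings = 24 ECGs per subject. With complete attendance:

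- 280 planned subjects: 280 × 24 = 6,720 tracings, and × 4 measures = 26,880 values. If triplicates are averaged first: 280 × 8 × 4 = 8,960 means.
- 268 subjects (28 active centres with one first-subset subject each, plus 240): 268 × 24 = 6,432 tracings, and × 4 = 25,728 values. Averaged: 268 × 8 × 4 = 8,576 means.

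A shift in the mean by dose cannot reasonably be read from a listing of that length.

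**The case against.** The strongest reply is that the safety information is mostly covered elsewhere, and much of this stands.

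- **Heart rate.** SAP 5.6.5.2 tabulates pulse rate at the same nominal times around both injections, with change from baseline and counts outside 40 to 100 bpm. A reader might infer that a heart-rate effect would be invisible. The documents do not support that; what is missing is the rate from the same tracings as the intervals.
- **Bazett.** A reader might also infer that the QTc Bazett table cannot be interpreted without ECG heart rate. That does not hold either. Fridericia is tabulated beside it, so a rate-driven rise would appear as Bazett moving while Fridericia stayed flat.
- **Adverse events.** Protocol 7.2.8 and 9.5.2 require clinically significant ECG changes to be reported as adverse events, and SAP 5.6.2.2 tabulates treatment-emergent events by dose and period. A PR or QRS abnormality judged significant would therefore reach a table. Shifts below that judgement would not, and they are the ones a dose comparison of means is meant to show.
- **Interpretations.** The SAP does not say that the central or investigator ECG interpretations are confined to listings. Its sentence concerns parameters. The supported statement is only that no summary of clinical significance is described.
- **Status of the protocol text.** The opening of Protocol Section 12 calls itself a summary to be fully described in the SAP. That allows the SAP to add detail. It does not cover dropping a stated analysis without declaring it.
- **Unseen material.** The contents of the ECG table list (SAP 6.1.3.4.1) and the attached shells are not available, so further ECG tables may exist there. If they do, they contradict the SAP text, which would still need correcting.

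**Conclusion.** The point holds as a gap in descriptive safety reporting. SAP 5.6.5.1 removes tabulation that Protocol 12.4 promises for 4 of 6 ECG measures, gives no summary by clinical significance, conflicts with its own change-from-baseline sentence, and is not declared in SAP Section 4. The loss falls mainly on PR, QRS and uncorrected QT. Mean shifts by dose in these, where not judged clinically significant, would appear in no summary described in the SAP text. Heart rate is a lesser loss because pulse rate partly covers it.

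The gap does not touch the primary analysis, any hypothesis test or the QTc summaries. It gives no reason to think that an ECG effect exists. It matters because the trial is meant to support the choice of a safe dose, and because correcting it costs little. The conclusion assumes that the SAP text governs what is produced, since the table list cannot be seen.

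**What to change.** In SAP 5.6.5.1, delete the listing-only sentence and state which measures the change-from-baseline sentence covers. Then add:

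- tables of PR, QRS, QT and ECG heart rate, using the triplicate mean, with value and change from baseline at each time point, by P03277 dose and for MultiHance®, in the column layout already set in SAP 5.6;
- counts of subjects with ECG changes judged clinically significant, in the same layout;
- counts of subjects outside normal range for these measures. The documents give no ranges for PR, QRS, QT or ECG heart rate, so the SAP must state them and their source before unblinding.

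If the sponsor prefers to keep any of these measures in listings only, SAP Section 4 should declare and justify that departure. This would make the plan transparent but would not restore the missing summary by dose.

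The cost is a few descriptive tables from data already collected, plus agreeing the ranges in advance. No test, sample size or primary result changes.
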